10. STATISTICAL ANALYSIS

Subjects' demographics, anthropometric measurements, medical history, alcohol consumption, lab test results, MELD score, quality of life, and other variables will be summarized by groups (case vs. control groups) and by visits. Mean and 95% confidence intervals will be calculated for continuous variables for each group. Proportion and frequency will be used to describe the categorical variables by groups. Two-sample t-tests will be used to compare the continuous variables and Chi-square tests will be used to compare the categorical variables by groups at each visit. Appropriate nonparametric test will be used if there is normal assumption violation. All the tests will be performed using SAS 9.3(Cary, NC).

More importantly, this aim serves as the backbone for conducting future clinical, mechanistic, biomarker discovery, therapeutic, and natural history studies. After a

structured process of requesting ancillary study proposals from consortium investigators, submitted proposals will be assessed for feasibility and scientific merit. For studies selected, a formal statistical plan will be developed that will include statistical models and methods to be used to address each specific aim of the study. Methods may be simple parametric or nonparametric methods for two-group comparisons such at t-tests or rank tests or may involve complex multivariable methods such as linear, logistic, or Poisson regression modeling. Each proposal must specify the primary and secondary outcomes. Sample size calculations associated with the primary analysis must be given, including clear specification of the outcome measure, error rates (Type I / II), minimal clinical important difference, and statistical power of at least 0.8. The expect amount and methods for dealing with missing data must be specified. Questions requiring longitudinal data analyses should apply statistical methods that account for, as applicable, time to events, repeated measurements, counts, or other discrete measurements. For time to event data, Cox proportional hazards regression model with appropriate covariates will be used. For hypotheses involving repeated measurements or discrete events, we will use either generalized linear models with generalized estimating equations or multilevel generalized linear mixed models with random coefficients.

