2. EXECUTIVE SUMMARY

Title

ALCOHOLIC HEPATITIS NETWORK OBSERVATIONAL STUDY

Study Type

Prospective, observational study

Investigational Sites

Indiana University in Indianapolis, IN, University of Louisville affiliated hospitals in Louisville, KY, Beth Israel Deaconess Medical Center (BIDMC) in Boston, MA, Mayo Clinic in Rochester, MN, Cleveland Clinic Foundation, in Cleveland, OH, University of Pittsburgh Medical Center in Pittsburgh, PA, University of Texas at Southwestern in Dallas, TX, and Virginia Commonwealth University in Richmond, VA.

Planned Number of Patients

Approximately 1260 (720 subjects with alcoholic hepatitis (AH), 360 heavy drinkers without significant liver disease, and 180 healthy controls) will be enrolled.

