3. KEY INCLUSION/EXCLUSION CRITERIA

CASES: Heavy drinkers with alcoholic hepatitis

Inclusion criteria

- 1. A clinical diagnosis of alcoholic hepatitis as defined by the NIAAA pan-consortia for AH:
 - a) Onset of jaundice (defined as serum total bilirubin >3 mg/dL) within the prior 8 weeks to screening visit
 - b) Regular consumption of alcohol with an intake of > 40 gm daily or >280gm weekly on average for women and > 60 gm daily or >420gm weekly on average for men for 6 months or more, with less than 8 weeks of abstinence before onset of jaundice
 - c) AST > 50 IU/I
 - d) AST:ALT > 1.5 and both values < 400 IU/I
 - e) and/or histological evidence of AH*
- 2. Serum total bilirubin >3 mg/dL
- 3. Subject or guardian ability to understand and willingness to provide written consent
- 4. Age greater or equal to 21 years
- 5. Re-enrolment of an alcoholic hepatitis donor is permissible up to 4 times if the donor presents with a new episode of alcoholic hepatitis 24 weeks or longer after the most recent enrolment in the study

Exclusion criteria

- Liver disease significantly caused by hemochromatosis, autoimmune liver disease, Wilson disease, and acute viral hepatitis (NOTE: The presence of chronic hepatitis C, hepatitis B, HIV, or stage 1 (one lesion <2 cm) HCC is not exclusion to participation)
- 2. Pregnant or breast feeding
- 3. Received liver transplant
- 4. Based on the judgment of the investigator, subject is not capable of understanding or complying with the study requirements

CONTROLS: Heavy drinkers without significant liver disease

Inclusion criteria

- 1. History of chronic alcohol consumption sufficient to cause liver damage. Generally, this is considered to be >40 g/day or >280g/week on average for women and >60 g/day or >420 g/week on average for men, for 6 months or more, with less than 8 weeks of abstinence. Judgement about chronic alcohol consumption will be made by the site investigator.
- 2. Subject or guardian ability to understand and willingness to provide written consent
- 3. Age greater or equal to 21 years

Exclusion criteria

1. Past evidence of alcoholic liver disease, defined as a bilirubin > 2.0 mg/dL, an AST > 1.5 ULN, and any hospital admission for liver disease, or the presence of

- esophageal varices or ascites (at any time in the past)

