4.3 Research and study procedures

4.3.1 Target enrollment:

90 patients with AH, 45 Heavy drinkers without significant liver disease and 22-23 healthy controls will be enrolled at each site. They will be followed for 24 weeks following their enrollment. The cohort will be characterized demographically, anthropometrically, clinically, through laboratory tests, and histologically wherever applicable.

4.3.2 Definitions:

Subjects with AH: We plan to enroll 720 patient with AH. The diagnosis of AH will be established on published criteria [6;10] and this is based on history of heavy alcohol consumption (defined as >40 g/day or >280g/week on average for women and >60 g/day or >420 g/week on average for men for 6 months or more, with less than 8 weeks of abstinence before onset of jaundice), clinical evaluation and appropriate laboratory testing (as defined as total bilirubin > 3 mg/dL and AST > 40 U/L). When the diagnosis of AH remains in question, a liver biopsy (if clinically feasible and subject has no contra-indications) will be required. A sizable proportion of individuals with AH have co-existing viral hepatitis or HIV, and there is an unmet need in terms of understanding the nature of their liver disease and to develop suitable therapies. Therefore, we plan to enroll patients with AH in special population infected with chronic HBV, chronic HCV, or HIV.

Heavily Drinking Controls: We plan to enroll 360 heavy drinking controls without significant evidence of liver disease at the time of recruitment. For this application, heavy alcohol drinking will be defined as >40 g/day or >280g/week on average for women and >60 g/day or >420 g/week on average for men for 6 months or more, with less than 8 weeks of abstinence before onset of jaundice. Heavy drinkers, who have just become abstinent within prior 2 weeks, including those we convince to seek alcohol abuse/addiction treatment as part of the recruiting process, are eligible for enrollment. The study team (investigators-coordinators) will emphasize to both

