4.3.4 Matching strategies

We will perform approximate frequency matching for recruiting control subjects using age, gender and race. The purpose of frequency matching is to ensure similar enough distributions between case and control groups to allow for appropriate statistical adjustment in the analyses. For every 30 heavy drinking controls the Data Coordinating Center (DCC) will evaluate the distribution of age (categories: 20-40, 41-60, 61-80, >80), gender, race (whites, blacks, others) overall and at each site. We will then compare that to the distributions of already recruited cases to determine if the distributions in age, gender, and race are similar. If the controls differ markedly, the DCC will instruct the coordinators to concentrate on recruiting the underrepresented groups in the control cohorts. The distribution of matching variables in the case and control groups will be re-examined periodically (approximately every 30 heavy drinking controls) and the control subjects will be recruited based on the updated distributions of demographic variables, as needed.

4.3.5 Variables and Data to be collected:

We will collect the following clinical details from subjects with AH and their controls (as appropriate). The detailed data collection and the questionnaires that we will use are outlined in the case report form (CRF).

- a) Demographics and anthropometric measures: These variables characterize the study cohort.
- b) Medical History: Detailed past medical history including prior history of AH. Specific

- attention will be paid to collecting family history of alcohol abuse and alcoholic liver disease and history of bariatric surgery.
- c) Medicinal history: A medication review of prescription and over the counter medications will be completed
- d) Detailed alcohol consumption history: We will use AUDIT, AUDIT-C and Time Line Follow-Back Questionnaires (TLFB) for quantifying alcohol consumption [11;12].
- e) Quality of life: We will use the Chronic Liver Disease Questionnaire (CLDQ) for quantifying quality of life.
- f) Signs and symptoms associated with liver disease and routine laboratories. These include the presence of ascites, jaundice, varices, and hepatic encephalopathy. Additionally, the subject's HBV, HCV and HIV status will be recorded, if available.
- g) Discriminant factor (DF), Model for End Stage Liver disease (MELD) score, and Child- Pugh score will be calculated [7].

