3. PARTICIPANT RECRUITMENT

Avenues of recruitment will be site specific for example: website, flyers, social media, craigslist, studykik, newspaper, and newsletters.

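### The core case-control comparisons in Section 10 ignore site although recruitment targets are set by site; stratifying by site costs almost nothing and protects them if the case:control ratio drifts between centres

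*Combined protocol and SAP*

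**What the plan says.** The Executive Summary (Section 2) names eight centres, starting with "Indiana University in Indianapolis, IN, University of Louisville affiliated hospitals in Louisville, KY, Beth Israel Deaconess Medical Center (BIDMC) in Boston, MA". It sets the study total: "Approximately 1260 (720 subjects with alcoholic hepatitis (AH), 360 heavy drinkers without significant liver disease, and 180 healthy controls) will be enrolled". Section 4.3.1 breaks this down by centre: "90 patients with AH, 45 Heavy drinkers without significant liver disease and 22-23 healthy controls will be enrolled at each site".

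Site enters the conduct of the study in several other places. Under Matching strategies (4.3.4) the coordinating center reviews the distribution of age, "gender, race (whites, blacks, others) overall and at each site". Under Participant Recruitment, "Avenues of recruitment will be site specific". For heavy-drinking controls the inclusion criteria give numerical intake thresholds and then add: "Judgement about chronic alcohol consumption will be made by the site investigator".

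Site does not enter the analysis. The first paragraph of Section 10 summarises by group and visit: "Mean and 95% confidence intervals will be calculated for continuous variables for each group". It then compares groups at each visit: "Two-sample t-tests will be used to compare the continuous variables and Chi-square tests will be used to compare the categorical variables by groups", with an unspecified nonparametric test if normality fails. The second paragraph mentions estimating equations and multilevel models, but for ancillary proposals with repeated measurements or discrete events, and it does not name site as a level.

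**The concern.** Subjects at one centre may resemble each other because they come through the same recruitment channels and the same local judgement. A two-sample t-test or chi-square test that ignores this is safe only while each centre contributes cases and controls in the same proportion. The plan aims at that proportion but has no rule that holds it. The study totals are approximate, the per-site numbers are targets, and the periodic check covers age, gender and race, not the case:control ratio. Tests are also run by visit. At week 24, when AH cases and heavy drinkers are both due, the ratio at each centre also depends on deaths and losses there. If the ratio varies, part of any AH-control difference may be a difference between centres.

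**Working it through.** **Plan's own figures.** 8 × 90 = 720, 8 × 45 = 360, 8 × 22.5 = 180, total 1260. The per-site targets reproduce the study totals.

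**Inputs.** From the documents: eight sites, with 90 AH and 45 heavy drinkers per site. Assumed, because the documents give no value: ICC ρ = 0.05, range 0.01 to 0.10; total SD 1; two-sided 5% level. The uneven enrolment patterns are also assumptions. Apart from the last pattern, they keep AH at 90 per site, and all keep the totals of 720 and 360.

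**Formula.** Let w₁ⱼ and w₂ⱼ be the shares of the AH and heavy-drinker groups enrolled at site j. With a site effect common to both groups:

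- True variance of the difference: T = ρ·D + (1 − ρ)(1/720 + 1/360), where D = Σ(w₁ⱼ − w₂ⱼ)².
- Expected variance used by the t-test: V = s₁²/720 + s₂²/360, where s² = (1 − ρ) + ρ(1 − Σwⱼ²) for each group.
- False-positive rate = 2[1 − Φ(1.96/√(T/V))].

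**Planned targets, ρ = 0.05.** All shares are 1/8, so D = 0. T = 0.95 × 0.0041667 = 0.003958. s² = 0.95 + 0.05 × 0.875 = 0.99375, so V = 0.004141. √(T/V) = 0.978 and the rate is 4.5%.

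**Controls at 60 in four sites and 30 in four, ρ = 0.05.** Control shares are 0.1667 and 0.0833 against 0.125 for AH. D = 8 × 0.04167² = 0.01389. T = 0.000694 + 0.003958 = 0.004653. V = 0.004139. √(T/V) = 1.060 and the rate is 6.5%.

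**All patterns, by the same formula:**

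| Heavy drinkers per site | D | ρ = 0.01 | ρ = 0.05 | ρ = 0.10 |
|---|---|---|---|---|
| 45 at every site (planned) | 0 | 4.9% | 4.5% | 4.0% |
| 54 at four, 36 at four | 0.0050 | 5.0% | 5.2% | 5.4% |
| 60 at four, 30 at four | 0.0139 | 5.3% | 6.5% | 8.0% |
| 80, 70, … down to 10 | 0.0324 | 5.8% | 9.1% | 13.3% |
| AH:controls 120:30 at four, 60:60 at four | 0.0556 | 6.5% | 12.5% | 19.3% |

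Simulation of the planned and the two most uneven patterns (20,000 runs each) agreed within 0.3 percentage points. A linear model with group and site held 4.8% to 5.2% throughout. At planned targets and ρ = 0.05, power at a standardised difference of 0.181 was 0.805 without the site term and 0.817 with it.

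**Limit of the site term.** Suppose the group difference itself varies between sites, and the inference is to other centres. At planned targets and ρ = 0.05, simulation with 0.5% of the variance group-by-site gave 8.0% for the naive test and 8.7% for the fixed-site model. With 1% the rates were 11.3% and 12.2%. A fixed site term does not cure this.

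**Group-mean intervals.** For the mean over these eight sites, the correct standard error is √(1 − ρ) of the naive one. At ρ = 0.05 that is 0.975, so the planned interval is slightly wide. For a wider population of centres, the design effect for AH is 1 + 89 × 0.05 = 5.45, and coverage is 2Φ(1.96/√5.45) − 1 = 60% (85% at ρ = 0.01, 47% at ρ = 0.10).

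**The case against.** The strongest reply is that under the plan as written the tests are sound. Every group is recruited at every site in the same proportion, so group is crossed with site and a common effect cancels. That stands. The higher rates come from enrolment patterns that depart from the targets, some of them extreme, and the coordinating center does monitor recruitment. That also stands: mild drift (54 and 36) costs almost nothing, and the 80-to-10 and 120:30 patterns mark the outer end, not a forecast.

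It can also be said that the study's objectives are a data resource and a specimen bank, with no primary hypothesis resting on this paragraph, and that ancillary studies will have their own statistical plans. Section 4.3.4 even anticipates statistical adjustment. This limits the consequence. It does not fill the gap, because Section 10 names no adjustment for the comparisons it does specify.

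Two stronger readings are tempting. One is that the 95% confidence intervals are too narrow. That needs both a positive ICC and inference beyond eight named centres. The documents give no ICC, describe no sampling of centres, and do not say which population the means describe. The aim of studying epidemiology and natural history hints at wider use but does not settle it. The other is that laboratory values are simply whatever each centre's routine care produced. Sections 5.2.1 and 5.2.2 say otherwise: blood count, hepatic function, INR and metabolic panel are reused if done within 30 days and otherwise performed by the study. Only the optional tests depend on routine care.

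**Conclusion.** The point holds as a modest improvement to the stated method. Section 10 compares groups without regard to a structure that the design itself sets up. At exact targets the cost is slight conservatism (4.0% to 4.9%). If the enrolled or retained ratio differs by site, the false-positive rate rises to about 5.2%, 6.5% or 9.1% at an assumed ICC of 0.05, depending on how uneven the controls are. These sizes rest on an ICC and on enrolment patterns that the documents do not supply, and on a site effect common to both groups.

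A reader might infer that the planned tests are already anti-conservative, or that the group-mean intervals are invalid. Neither is supported. The tests are safe at the planned ratio, and the intervals are valid, and slightly wide, for the enrolled sites.

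**What to change.** In the first paragraph of Section 10:

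1. Compare groups at each visit with site as a stratum: a linear model with group and site for continuous variables, the van Elteren test as the nonparametric fallback, and the Cochran-Mantel-Haenszel test stratified by site for categorical variables.
2. Report a check of group-by-site variation with these comparisons, since the site term does not protect against it.
3. Label the group means and 95% confidence intervals as describing the enrolled sites. If inference to other centres is intended, say so and use a site-level interval with t on 7 degrees of freedom (8 sites − 1).

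The data are already collected, so the cost is wording and a few lines of SAS. The AH versus heavy-drinker model loses 7 residual degrees of freedom (1080 − 2 = 1078 becomes 1080 − 9 = 1071). The site-level interval in item 3 would be clearly wider with only eight centres, so it is a choice for the sponsor and not a required correction.

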The collection of clinical information and biosamples in subjects with AH are very crucial to pursue research and advance the science in the field of alcoholic liver disease. The current protocol provides a system to uniformly obtain demographics, clinical information, and biological samples from AH subjects and well-matched controls with heavy alcohol use without clinical presentation of AH and heathy controls for future investigations. In addition, they will serve as the potential subjects to be enrolled in the future clinical trials of the AlcHepNet consortium.

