5.2 Follow up visits

Alcoholic hepatitis cases: will be seen at (week 4), (week 12), (week 24). During these follow-up visits, data on clinical characteristics, alcohol use, and biosamples will be obtained. If a patient misses a follow-up visit, the patient will be called and the data will be collected from their medical records (if available). Cases will then be followed until the end of study after their final visit (week 24) by checking their medical record. Vitality status will also be checked via National Death Index to ensure survival status could be collected for subjects who could not be followed through medical record review.

Heavy drinking controls without significant liver disease: The second part consists of a follow-up visit during week 24, data on clinical characteristics, alcohol use, and biosamples will be obtained.

Healthy Controls: There will be no follow-up visits

Table 2. Study procedures during the baseline and follow up visit.

Procedures	Baseline ¹	Week 4 (D15 - D56)	Week 12 (D57 - D 126)	Week 24 (D127 - D 252)	Every 24 weeks for a maximum of 5 years
Source of data	Patient visit & medical records	Patient visit, medical records ±phone call	Patient visit, medical records ±phone call	Patient visit, medical records ±phone call	Medic al Recor ds
Group	AH, Drinking Controls, and Healthy Controls	АН	АН	AH and Drinki ng Contro Is	АН
Informed Consent	X				
Demographics	X				
Anthropometric measurements	X	X	X	X	
Vital Signs	Χ	X	Χ	Χ	
Medical history	X				
Alcohol use History	X	X	Χ	X	
Questionnaires ³	Х	Χ	Χ	Χ	
Con-Med Review	Χ	X	X	X	
Events of Special Interest ⁵		Х	X	Х	
General PE	X				
PE (liver-related)		X	Χ	X	
Blood tests and other pr		1	T	Las	r
Hepatic Function	X	X	X	X	
Basic metabolic panel	X	X	X	X	
Hematology/CBC	X	X	X	X	
Coagulation/INR	X	Х	X	X	
Infection screen ²	X				
Imaging/X-ray ² Endoscopy ²	X				
Fibroscan or other ⁴	X			X	
Pregnancy Test, Urine	X	X	X	X	
Research Specimen Coll			Ι Λ	Ι Λ	
Plasma	X	Х	Х	Χ	
Serum	X	X	X	X	
Stool (when available)	X	X	X	X	
Saliva ⁶	X		X		
Urine (when available)	X	Χ	X	Χ	
Liver Biopsy (when available)	X	X	X	X	
PBMC (optional by site)	Х	Х	Х	Х	
DNA (if patient consents)	Х				
Survival, from medical records, phone call or					X
death indices					

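### Controls are matched only approximately so that analyses can adjust, yet the main-study group tests in Section 10 are unadjusted; a modest gap with a nearly free remedy

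*Combined protocol and SAP*

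**What the plan says.** Section 4.3.4 plans approximate frequency matching of controls on age, gender and race. Its stated purpose is to "ensure similar enough distributions between case and control groups to allow for appropriate statistical adjustment in the analyses". The coordinating centre will "evaluate the distribution of age (categories: 20-40, 41-60, 61-80, >80), gender, race (whites, blacks, others) overall and at each site", roughly after every 30 heavy drinking controls, and redirects recruitment only when the difference is marked. No numeric tolerance is given, and no such trigger is stated for healthy controls.

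Section 10 describes summaries by group and visit and then gives the main-study tests: "Two-sample t-tests will be used to compare the continuous variables and Chi-square tests will be used to compare the categorical variables by groups". These are repeated visit by visit, and a nonparametric test replaces them if normality fails. No covariate is mentioned.

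The rest of Section 10 concerns ancillary proposals, each of which gets its own statistical plan:

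- Linear, logistic and Poisson regression are optional: "Methods may be simple parametric or nonparametric methods for two-group comparisons such at t-tests or rank tests or may involve complex multivariable methods".
- Cox regression is firm: "For time to event data, Cox proportional hazards regression model with appropriate covariates will be used".
- Generalized estimating equations (GEE) or mixed models are likewise firm for repeated measurements or discrete events.
- None of this names age, gender or race.

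**The concern.** Frequency matching in 20-year age bands makes adjustment feasible; it does not replace it. Within-band age differences, and whatever imbalance remains between bands, carry straight into an unadjusted t-test or chi-square test.

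The comparisons most exposed are those of variables that eligibility does not largely determine: baseline quality of life, most blood-count and metabolic-panel values, and, between AH and heavy drinkers, anthropometrics and quantity of alcohol consumed. For these, part of an observed group difference could reflect age, gender or race rather than disease. Section 10 goes beyond summaries to hypothesis tests, and the data-management section gives the coordinating unit the analyses for abstracts and manuscripts, so such differences may be published as they stand.

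**Working it through.** **Inputs from the documents.** Group sizes are 720 AH, 360 heavy drinkers and 180 healthy controls (Section 2). They sum to the stated 1260. The per-site targets in Section 4.3.1 agree over the eight listed sites: 8 × 90 = 720, 8 × 45 = 360, and 8 × 22 to 8 × 23 = 176 to 184, which brackets 180. The main study states no alpha, power or effect size, so there is no power figure to reproduce.

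**Assumed inputs.** Two-sided 5% test; age-outcome correlation r = 0.1 to 0.3; residual age gap d = 0 to 0.2 SD. A gap near 0.2 SD is plausible: if 10% of controls sit one 20-year band away, mean age shifts by 0.10 × 20 = 2.0 years, which is 0.13 to 0.20 SD for an assumed age SD of 15 to 10 years. At a check on 30 controls, a band share of 50% has a 95% half-width of 1.96 × √(0.25/30) = 17.9 percentage points. At 45 (one site) it is 14.6 and at 360 it is 5.2. Early and site-level checks are therefore coarse.

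**Bias and standard error, in outcome SD.** Bias = r × d. SE = √(1/n₁ + 1/n₂), which is 0.0645 for 720/360 and 0.0833 for 720/180.

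**Rejection rate with no true difference.** Φ(−1.96 + bias/SE) + Φ(−1.96 − bias/SE):

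| r | d | 720/360 | 720/180 |
|---|---|---|---|
| any | 0 | 5.0% | 5.0% |
| 0.1 | 0.1 | 5.3% | 5.2% |
| 0.1 | 0.2 | 6.1% | 5.7% |
| 0.2 | 0.1 | 6.1% | 5.7% |
| 0.2 | 0.2 | 9.5% | 7.7% |
| 0.3 | 0.1 | 7.5% | 6.5% |
| 0.3 | 0.2 | 15.3% | 11.1% |

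**When the true difference is not zero.** At the top corner the estimate shifts by 0.3 × 0.2 = 0.06 SD. That is 0.06/0.0645 = 0.93 SE or 0.06/0.0833 = 0.72 SE, so a 95% interval covers 100 − 15.3 = 84.7% or 100 − 11.1 = 88.9% of the time.

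**Does adjustment repair it?** In 20,000 simulated studies at that corner, with continuous age, gender and race in the model, the rejection rate fell from 15.5% to 5.0% (720/360) and from 11.4% to 5.3% (720/180).

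**Price in precision.** SE factor = √[(1 − R²)(1 + D² p(1 − p))], where R² is the outcome variance explained by the covariates, D² the sum of squared covariate gaps (covariates taken as uncorrelated) and p the control share.

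- Top corner, 720/360 (R² = 0.09, D² = 0.04, p = 1/3): √(0.91 × 1.0089) = 0.958, a gain of about 4%.
- R² = 0, three covariates each 0.3 SD apart (D² = 0.27): 1.030 at p = 1/3 and 1.021 at p = 1/5.
- R² = 0, three covariates each 0.5 SD apart (D² = 0.75): √(1 + 0.75 × 2/9) = 1.080 and √(1 + 0.75 × 4/25) = 1.058.

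**The case against.** The strongest reply is that adjustment is deferred rather than forgotten. The objectives are to store data and build a specimen bank. The main study has no hypothesis, primary outcome, alpha or power, and its tests accompany descriptive summaries. Section 4.1 describes "well-matched controls with heavy alcohol use without clinical presentation of AH and heathy controls for future investigations", so the analyses meant in Section 4.3.4 may be those of later studies, each with its own plan. Section 10 also commits those studies to Cox models with covariates and to GEE or mixed models where the data call for them.

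Most of this stands. A reader might infer that the protocol contradicts itself, or that it never adjusts. The documents do not support either reading, because Section 4.3.4 can be satisfied by later plans. What remains is narrower: the group tests Section 10 does commit to are unadjusted on any reading, and the ancillary text neither requires linear or logistic adjustment nor names the matching factors.

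A reader might also infer that the main-study results will be seriously biased. That does not follow. The correlation and age gap are assumed, most cells of the table lie between 5% and 8%, and the false-positive rate matters only where the true difference is near zero. Many contrasts between jaundiced patients and people selected for no significant liver disease, or for general health, will be large.

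Finally, adjustment for three factors cannot remove differences that eligibility creates, and these probably dominate AH against healthy controls. That is a fair limit on the benefit.

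**Conclusion.** The point holds in a limited form. The main-study comparisons omit the adjustment that the matching was meant to permit. The consequence is modest: a bias of up to 0.06 SD and rejection rates of 5 to 15% (720/360) or 5 to 11% (720/180) for a nominal 5% test, under r = 0.1 to 0.3 and a gap of 0 to 0.2 SD. The upper ends need both assumptions at their maximum; with no residual imbalance the rate stays at 5%. The figures treat age alone, since the documents give no expected imbalance for any factor.

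The change is worth making because the covariates are already recorded at baseline, not because the study is at risk.

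Two neighbouring matters are separate from this point: repeat enrolment of AH subjects ("Re-enrolment of an alcoholic hepatitis donor is permissible up to 4 times if the donor presents with a new episode"), and heavy drinkers' follow-up, where Section 5.2 and Table 2 give one visit ("The second part consists of a follow-up visit during week 24") and Section 5.2.2 gives weeks 4, 12 and 24. Those visit passages must be reconciled.

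**What to change.** Amend Section 10 as follows.

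- Keep unadjusted summaries and tests for demographics and for checking the matching.
- For the other variables, state in advance that the leading comparison is a regression on group adjusted for continuous age, gender and race: linear for continuous outcomes, logistic for binary ones, multinomial or ordinal for more than two levels. Give AH against heavy drinkers and AH against healthy controls as separate contrasts. Report the unadjusted result as supportive, so that neither is chosen after the fact.
- For skewed outcomes, use a transformed or rank-based adjusted model in place of the unadjusted nonparametric test. For binary outcomes, name the adjusted measure, for example a conditional odds ratio or a standardised risk difference.
- State that adjustment does not remove differences created by eligibility: bilirubin, INR and hence MELD; AST and ALT, which AH entry criteria also constrain; and, for healthy controls, alcohol intake, haemoglobin, treated diabetes, BMI and the other comorbidity exclusions.

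The cost is SAP wording and a little analysis work, with no added participants, visits or data. If the covariates do not predict the outcome, the SE is about 2 to 3% larger with three covariates each 0.3 SD apart, or about 6 to 8% larger at 0.5 SD. With no matching tolerance stated, neither figure is an upper bound. Where age does predict the outcome, as in the 720/360 corner case above, the SE falls by about 4%.
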